## 1.0 Study Summary

Study Title	Short Term Choline Supplementation and Cardiovascular Health in Adults
Study Design	2 x 4 crossover design with repeated measures and we will conduct descriptive univariate analyses on all study variables.
Primary Objective	To establish proof-of-concept for a greater reduction in glucose homeostasis following increases in gut microbiota-generated TMAO on glucose homeostasis in older compared with young adults in order to conduct a larger, more comprehensive and mechanistic trial in the future.
Secondary Objective(s)	- Obtain preliminary data for effect size generation.
Study Population	We are recruiting men and women who are between the ages of 18-79 years of age. We will recruit individuals of all races and ethnic backgrounds.
Sample Size	60 subjects
Research Intervention(s)/ Investigational Agent(s)	-Interventions (Choline and Placebo supplementation in capsule form)
Study Duration for Individual Participants	
How long will a participant spend in your study? If multiple sessions, list time required for each session plus total.
 
Visit: 1 = 1 hour
 
Visit: 2, 8, 11, 17 = 3 hours each
 
Visit: 3, 9, 12, 18 = 2 hours each
 
Visit: 4, 10, 13, 19 = 3 hours each
 
Visit: 5, 6, 7, 14, 15, 16 = 30 minutes each
 
Total Time: 36 hours

Acronyms and Definitions	
TMA = Trimethylamine
 
TMAO = Trimethylamine-N-oxide
 
T2D = Type 2 Diabetes
 
GI = Gastrointestinal
 
FMD = Flow mediated dilation
 
CGM = Continuous glucose monitor

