## 2.0 Objectives

### 2.1 Describe the purpose, specific aims, or objectives of this study:

To establish proof-of-concept for a greater reduction in glucose homeostasis following increases in gut microbiota-generated TMAO on glucose homeostasis in older compared with young adults in order to conduct a larger, more comprehensive and mechanistic trial in the future.

*2.2 State the hypotheses to be tested:*

We hypothesize that gut microbiota-generated increases in plasma TMAO will be greater in older compared with young adults and this will be associated with a correspondingly greater reduction of insulin sensitivity, mixed meal tolerance, and 24-hr glycemic control in older adults.

In addition, we hypothesize that the magnitude of change in gut microbiota-generated increases in TMAO and measures of insulin sensitivity, mixed meal tolerance, and 24-hr glycemic control with the intervention will be associated with the magnitude of change in the abundance of TMA-producing bacteria and/or expression of cutC TMA lyase.

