## 5.0 Study Design and Statistical Analysis Plan

5.1 *Describe the basic study design/approach (e.g., qualitative study using five focus groups of first year students to describe assimilation into the university community; randomized controlled trial of a behavioral change*

*intervention to increase dietary intake of whole grains; pre- post-test evaluation of new pedagogical techniques to improve adult literacy):*

A double-blind randomized 2x3 crossover design with 3 repeated measures in each period will be used. Pre-/post-test evaluation used in each period to evaluate the ingestion of choline/placebo on the effects to cardiometabolic health.

**5.2** *Describe corresponding data analysis plan/approach (e.g., content analysis of focus group transcripts; descriptive analysis followed by linear regression modeling; nonparametric analysis of pre- and post-test measures):*

Data will be examined for the presence of outliers, violations of normality and missing data. Major violations of normality will be corrected with an appropriate transformation procedure. In case of an outlier, rather than transform the data, the outlier will be “Winsorized”, that is, replaced by the most extreme value in the tail of the distribution. Data will be checked for sequence, period and carryover effects. Next, a mixed-effects linear model (using SAS PROC MIXED) will be used to estimate the treatment differences between choline and placebo ( $H_0: \mu_{AB} - \mu_{BA} = 0$ ). Because of the two repeated measurements of the dependent variable in each period, we will treat the multiple observations as nested within individuals. This will allow us to model the various sources of intra-person and inter-person variability, as well as account for the correlation in the nested data to make the correct inference regarding differences between treatments. Confidence intervals (95%) and bootstrapped standard error estimates will be reported for statistical precision and estimation of effect sizes for a larger more comprehensive trial. An identical approach will be used for analysis of other outcomes (e.g., arterial stiffness, etc.).

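### The analysis plan specifies no age term for its primary older-versus-young comparison, and no pre/post term for the two measurements in each period

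*Combined protocol and SAP*

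**What the plan says.** **The question.** The primary objective in the Study Summary (1.0) is proof of concept for a "greater reduction in glucose homeostasis following increases in gut microbiota-generated TMAO on glucose homeostasis in older compared with young adults". Hypothesis 1 in 2.2 says that TMAO increases "will be greater in older compared with young adults and this will be associated with a correspondingly greater reduction of insulin sensitivity". Section 4.1 repeats this as the endpoint statement.

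**The model.** Section 5.2 gives one model: "a mixed-effects linear model (using SAS PROC MIXED) will be used to estimate the treatment differences between choline and placebo". The null is printed as mu_AB - mu_BA = 0. Before the model, "Data will be checked for sequence, period and carryover effects". The same approach is extended to the other outcomes. On the structure of the data, 5.2 says: "Because of the two repeated measurements of the dependent variable in each period, we will treat the multiple observations as nested within individuals".

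**The design.** Section 5.1 says "A double-blind randomized 2x3 crossover design with 3 repeated measures in each period will be used", and then "Pre-/post-test evaluation used in each period to evaluate the ingestion of choline/placebo on the effects to cardiometabolic health". Hypothesis 2 in 2.2 concerns "the magnitude of change in gut microbiota-generated increases in TMAO and measures of insulin sensitivity, mixed meal tolerance, and 24-hr glycemic control".

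**The participants.** Section 12.2 admits a single age range, 18 to 79. Section 14.1 enrols 60 in total and gives no number by age.

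**The concern.** The primary question is a difference between two age groups in the effect of choline. The plan's only model is aimed at the overall effect. An analyst who follows 5.2 will finish without an estimate, an interval or a test for the contrast the pilot was set up to explore, and could choose the age cut-off after seeing the data.

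The second gap concerns the response variable. Section 5.2 calls the pre-supplement and end-of-period values repeated measurements of the dependent variable and deals with them by nesting. Nesting describes correlation. It does not tell the model that one of the two rows precedes exposure. The pilot is meant to supply effect sizes for a larger trial (5.2, 14.1), so two analysts who read 5.2 differently could pass on effect sizes that differ by a factor of two.

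**Working it through.** **1. Where age appears.**

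- Older versus young is the question in 1.0, 2.1, 2.2 (hypothesis 1) and 4.1.
- Section 5.2 names treatment, and sequence, period and carryover as checks. Age is not mentioned.
- Section 1.0 adds only descriptive univariate analyses.
- Section 12.2 gives one range, with no cut-off for older or young.
- Section 14.1 gives 60 in total, with no split by age.

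The overall effect cannot stand in for the age contrast. Let d_Y and d_O be the choline effects in young and older adults, and w the proportion who are young. A treatment difference without an age term estimates w·d_Y + (1-w)·d_O. With an assumed w = 0.5:

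- d_Y = 20 and d_O = 20: overall 20, age difference 0.
- d_Y = 10 and d_O = 30: overall 20, age difference 20.

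The overall estimate is the same in both cases, and only an age-by-treatment term separates them.

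**2. What the two measurements are.** In 8.2 the oral glucose tolerance test is done at sessions 2, 8, 11 and 17. Capsules are first handed out at session 4, and the washout follows session 10. Sessions 2 and 11 are therefore the pre-supplement values, and sessions 8 and 17 the end-of-period values.

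**3. What follows if both rows are treated as outcomes.** Section 14.1 powers the study on 20 ± 32%; 20/32 = 0.625, which agrees with its stated effect size of 0.63. Take 20 as the true effect, in absolute value, and assume no carryover. Expected departures from a common level are:

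| | Pre | End of period | Mean of both rows |
|---|---|---|---|
| Choline period | 0 | 20 | (0+20)/2 = 10 |
| Placebo period | 0 | 0 | (0+0)/2 = 0 |

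- Treatment main effect on both rows: 10 - 0 = 10.
- Change score or treatment-by-time: (20-0) - (0-0) = 20.
- End-of-period value: 20 - 0 = 20.

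The factor of one half does not depend on the correlations.

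A simulation of 300 trials agrees. It assumed 60 participants, half of them older; effects of -10 in the young and -30 in the older; and standard deviations of 25 between participants, 8 for participant-by-period and 16 residual. The mean estimate was -9.9 with treatment and period only, and -20.1 for treatment-by-time. The 20-point age difference was recovered (-20.1) by a treatment-by-time-by-age term.

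**4. Counts and null hypothesis.** Two periods with two values each make 2 × 2 = 4. That agrees with 5.2 (two per period), 14.1 (four) and the schedule. Section 5.1, with 2x3 and three per period, is the outlier; it may be a slip from the three-day testing sessions in 8.1. The labels AB and BA are not defined. If they are sequences, as is usual in crossover notation, each sequence contains both treatments once, so the treatment effect cancels from the difference in sequence means.

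**The case against.** **The halving needs an unlikely analyst.** Someone would have to use a pre-supplement value as an outcome, code it with a treatment not yet taken, and report the main effect. Section 5.1 speaks of pre/post evaluation, 2.2 speaks of magnitude of change, and 5.2 does not list its fixed effects, so a pre/post factor may have been intended. This stands. A reader might infer that the trial will report half the true effect; the documents do not support that. They show only that 5.2 specifies no such term and does not exclude the reading. Section 14.1 is weak support either way, because its change could mean a choline-placebo difference.

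**A loss of power or a carryover bias.** A reader might also infer that 60 participants are too few for the age contrast, or that carryover will distort the baselines. The documents give no correlations, no age split and no figure for persistence. A two-week washout is planned and carryover is to be checked. Neither inference can be given a size from the text.

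**It is a pilot.** True, but proof of concept for the age difference is the stated primary objective, so pilot status does not excuse leaving that contrast without an estimate.

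**The choice of estimator is preference.** Largely fair. What the documents require is that one response be named. An age-by-treatment term also leaves untested the associations in 2.2 between TMAO, glycaemic measures and gut bacteria.

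Nothing in the objections answers the missing age term.

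**Conclusion.** The main point holds without numerical assumptions: the plan as written does not specify an estimate or test of its primary older-versus-young contrast, nor the age groups or group sizes needed for one.

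The second point holds in a limited form. Section 5.2 does not specify how the pre-supplement value enters the model. Under a reading it leaves open, the estimate would be 10 instead of 20. That figure assumes no carryover, the pre row coded with that period's treatment, and the main effect reported. Other sections point away from that reading, so it is a risk from under-specification, not a predicted result.

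The repeated-measures count in 5.1 and the labels in the null hypothesis are smaller wording faults. The whole point should be fixed before the data are analysed.

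**What to change.** Replace the model description in 5.2 with an explicit one:

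- **Response:** the end-of-period value, adjusted for the period-specific pre-supplement value and the participant's mean pre-supplement value. A change score, or treatment-by-time on all four rows, is also acceptable; the plan should name one.
- **Fixed effects:** treatment, period, sequence, age group and age-group-by-treatment. **Random effect:** participant.
- **Primary hypothesis:** tested by the age-group-by-treatment term (treatment-by-time-by-age if all four rows are modelled) and reported with its 95% confidence interval.
- **Overall null:** mu_choline - mu_placebo = 0.
- **Age:** define the groups and their intended sizes, or use continuous age.
- **Sensitivity analysis:** the same model without the pre-supplement covariates.

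In 5.1, correct the 2x3 label and the three measures per period to two periods with one pre and one post value each.

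The cost is wording; the baselines are already collected. The model spends a few degrees of freedom on the baseline and age terms. Baseline adjustment is sensitive to carryover into the second-period baseline. The sensitivity analysis checks this, but only for carryover that has gone by the end of the second period.

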## **6.0 Setting**

**6.1** *Describe the sites or locations where your research team will conduct the research. Consider each of the items listed below:*

- *Identify where your research team will identify and recruit potential subjects.*
- *Identify where the team will perform the research procedures.*
- *Describe the composition and involvement of any community advisory board(s).*
- *For research conducted in other locations, describe:*
  - *Site-specific regulations or customs affecting the research at those locations.*
  - *Local scientific and ethical review structure at those locations. Examples include work in other cultures or ethnic groups (within or outside of the U.S.) and work with churches. The*

*HRPP will provide additional guidance for international research.*

- Subjects will be recruited from the New River Valley and surrounding areas.
- The study will be conducted in the Department of Human Nutrition, Foods, and Exercise at Virginia Tech, Blacksburg, VA. Participants will be required to come to Garvin Building, Suite 1575 ([name]) for 19 visits.

## **7.0 Study Intervention(s)/Investigational Agent(s)**

*7.1 Describe the study interventions (including behavioral interventions) and/or investigational agents (e.g., drugs or devices) to be used in this study. Consider each of the items listed below:*

- *Drug/Device Handling: If the research involves drugs or devices, describe your plans to store, handle, and administer the drugs or devices so that they will be used only on subjects, and only by authorized investigators.*
- *Describe whether any of the following will be used: microwaves, X-rays, DEXA scans, general anesthesia, or sedation*
- *If control of the drugs or devices used in this protocol will be accomplished by following an established, approved organizational SOP (e.g., Research Pharmacy SOP for the Control of Investigational Drugs, etc.), please reference the SOP in this section.*

This study will utilize the use of choline supplement (500mg BID capsules) and a same look/taste placebo supplement (500mg BID capsules) randomized in a double blinded trial as interventions.

The choline and placebo supplements will be stored and locked away in the Human Integrative Physiology Lab and only members of the research team will have access to these capsules. Once subjects are required to be provided with the choline or placebo supplement, they will be provided to the participants in sealed containers which are assigned by subject ID. Only members of the research team will provide the supplements to the subject.

The capsules will be produced in aseptic conditions in the Human Integrative Physiology Laboratory by members of the research team.

DEXA scans will be used as part of a body composition analysis required on four visits (Visit 3, 9, 12, 18). The amount of radiation that a DEXA exam incurs is less than the amount permitted by the Food and Drug Administration (FDA) per year. The amount that will be received is equal to  $4*1/20$  of a chest x-ray.

*7.2 List the name of all drugs (including any vitamins, supplements, herbs, or nicotine) to be used in the study. Indicate whether they have FDA approval, and list any limitations for their use:*

Choline: Choline is a water-soluble vitamin-like essential nutrient that is available as an over-the-counter supplement. Adequate intake for adults is 550 mg/day for men and 425 g/day for women. Tolerable upper intake level for adults is 3500 mg/day. Doses over the daily upper intake levels may cause side effects such as sweating, a fishy body odor, gastrointestinal distress, diarrhea, and vomiting. Some individuals might be allergic to choline or the other ingredients. Individuals who have known allergies to choline or other ingredients will be excluded. The subjects always will have the ability to terminate their participation for any reason without consequence. The dose of 1000 mg/day dose of choline bitartrate USP (500 mg BID; NutriScience, Trumbull, CT) provided is well below the tolerable upper intake level for adults. Choline bitartrate USP is available as an over-the-counter supplement and is Generally Recognized as Safe by the FDA.

Placebo: This will mimic the look of the choline capsule and contains 1000 mg (500 mg BID) of maltodextrin, a polysaccharide or carbohydrate commonly found in foods in a normal diet.

Nitroglycerin: These are stabilized sublingual compressed tablets which will contain 0.4mg of nitroglycerin and are FDA approved.

*7.3 List all devices, how they will be used, their purpose in the study, and if they will be used in a manner consistent with their approved uses. If they will be used in ways that are not yet FDA approved, indicate whether they need an IDE or a determination that they are exempt from the IDE Determination. If a determination of significant risk or non-significant risk is needed for any of the devices, include the researcher's recommendation for each of those devices:*

- To perform the FMD portion of the investigation, duplex ultrasonography will be used. To perform this, a GE Vivid S6 unit equipped with a high-resolution linear array transducer will be used in accordance with published guidelines. Furthermore, carotid imaging will be performed using the same unit to obtain carotid artery diameters.

- To perform the arterial stiffness measurements, applanation tonometry will be used. A fingertip probe which is equipped with a high-fidelity strain gauge transducer will be placed on the carotid, brachial, radial, and femoral arteries to obtain pressure waveforms and amplitudes. Again, this procedure will be performed following published guidelines.
- Continuous measurements of glucose will be assessed using the FreeStyle Libre Pro, Abbott CGM. It will be placed on the upper back side of an arm. This will be performed following the guidelines and protocol from the device's company (Abbott).
- Blood pressure measurements will be obtained using a mercury sphygmomanometer or automated blood pressure monitor and these measurements will strictly conform to American Heart Association guidelines.
- Body composition analysis will be obtained via a DEXA scan with a Prodigy Advance, GE Healthcare unit. This will be performed only by trained and certified technicians and the amount of radiation that a DEXA exam incurs is less than the amount permitted by the FDA per year.

**7.4 If the drug is investigational (has an IND) or the device has an IDE or a claim of abbreviated IDE (non-significant risk device), include the following information:**

- *Identify the holder of the IND/IDE/abbreviated IDE.*
- *Explain procedures followed to comply with sponsor requirements for FDA regulated research for the following:*

FDA Regulation	Applicable to:		
	IND Studies	IDE studies	Abbreviated IDE studies
21 CFR 11	X	X	
21 CFR 54	X	X	
21 CFR 210	X		
21 CFR 211	X		
21 CFR 312	X		
21 CFR 812		X	X
21 CFR 820		X	

IDE exempt

## **8.0 Procedures Involved**

*8.1 Describe and explain the study design:*

Using a randomized cross-over design, participants will be given and asked to consume either choline or a placebo (maltodextrin) supplement for four weeks and will consume 1000 mg (500 BID) of choline or placebo per day. Testing will take place over twelve visits. Participants will complete a screening visit and two periods of three-day testing sessions before and after the four-week period of choline and placebo supplement. In between experimental sessions, there will be a two-week “washout”.

*8.2 Provide a description of:*

- *All research procedures being performed*
- *If the study has more than one procedure, session, and/or subject population, describe each procedure, session, and/or study population separately. For complex studies, you are encouraged to include a figure or chart.*

Session 1: Baseline (screening) session (Approximately 2 hours) Garvin Building, Suite 1575

Overnight Fast: Subjects will be asked to avoid eating or drinking anything except water and to avoid consuming any caffeine-containing beverages for 12 hours prior to this visit so that the test results will not be influenced by the food they eat or by the normal digestion process.

Blood Chemistry: A blood draw will be collected for choline concentrations as well glucose, cholesterol, and other factors that may impact or be reflective of vascular function/health. A needle will be inserted in an arm vein to draw blood (approximately 2 tablespoons/draw).

Urine Test: Subjects will be asked to urinate in a small cup. Sodium and other electrolytes, glucose, protein, pH, and whether there are blood cells present will be measured to determine whether it is safe for each individual to participate in the study.

Proof of COVID-19 vaccination: Subjects will be asked to bring their vaccination card against COVID-19 to the laboratory.

Medical History: Subjects will be asked to complete a medical history questionnaire, which will be used to screen for health problems (unstable heart disease) or other reasons (medications which influence study results) that would preclude participation.

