## VT 18-535 Short Term Choline Supplementation and Cardiovascular Health in Adults

**Stool Collection:** Subjects will be given a test tube and asked to collect a stool sample. Subjects will be asked to bring the sample back to the laboratory during their next scheduled visit. All supplies and instructions will be provided by the laboratory.

**Continuous Glucose Monitoring:** Glucose will be measured by a continuous glucose monitor (FreeStyle Libre Pro, Abbott). A small sensor will be placed on the subject's skin overlying the back side of their arm in order to measure glucose continuously. The sensor has a small plastic tube that is inserted into the tissue just below the skin and is held in place with sticky tape. The device will be worn for 3-4 days.

Session 3, 9, 12, 18: (Approximately 2 hours) Garvin Building, Suite 1575

**Overnight Fast:** Subjects will be asked to avoid eating or drinking anything except water and to avoid consuming any caffeine-containing beverages for 12 hours prior to this visit so that the test results will not be influenced by the food they eat or by the normal digestion process.

**Resting Blood Pressure and Heart Rate:** Blood pressure measurements will be made under quiet, comfortable ambient laboratory conditions via mercury sphygmomanometry or an automatic blood pressure monitor. Heart rate will also be determined by an automatic blood pressure cuff. Measurements will conform strictly to American Heart Association guidelines.

**Body Mass:** Body weight will be measured on a digital scale accurate to +/- 0.01 kg.

**Dietary intake analysis (24-hour recall):** Subjects will be asked to recall all the food and beverages they consumed in the previous 24-hour period.

**Blood Chemistry:** A blood draw will be collected for choline concentrations as well as glucose, cholesterol, and other factors that may impact or be reflective of vascular function/health. A needle will be inserted in an arm vein to draw blood (approximately 2 tablespoons/draw).

**Arterial Stiffness:** Carotid Ultrasonography - Common carotid artery diameters will be measured from the image obtained from an ultrasound unit (GE Vivid S6) equipped with a high-resolution linear array transducer. Applanation Tonometry - The carotid, brachial, radial and femoral artery pressure waveform and amplitude will be obtained by a fingertip probe incorporating a high-fidelity strain gauge transducer.

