## VT 18-535 Short Term Choline Supplementation and Cardiovascular Health in Adults

Endothelium Independent Vasodilation: This will be assessed by measuring brachial arterial dilation for 5 minutes following administration of 0.4 mg of sublingual nitroglycerine. Individuals will not be allowed to participate in this aspect if they take Cialis or Viagra or have a history of coronary heart disease.

24-hour Urine Collection: Subjects will be asked to collect all urine samples over a 24-hour period and bring the sample back to the laboratory during their next scheduled visit. All supplies and instructions will be provided by the laboratory.

Body Mass and Composition: Body weight will be measured on a digital scale accurate to +0.01 kg. Height will be measured with a stadiometer. Percent body fat and fat-free mass will be measured in all subjects using dual-energy x-ray absorptiometry (DEXA) (Prodigy Advance, GE Healthcare).

Pregnancy Test: If a subject is female and pre- or peri-menopausal or not postmenopausal for at least 1 year, she will be required to provide a small cup of urine for a pregnancy test.

Session 4, 10, 13, 19: (Approximately 3 hours) Garvin Building, Suite 1575

Overnight Fast: Subjects will be asked to avoid eating or drinking anything except water and to avoid consuming any caffeine-containing beverages for 12 hours prior to this visit so that the test results will not be influenced by the food they eat or by the normal digestion process.

Resting Blood Pressure and Heart Rate: Blood pressure measurements will be made under quiet, comfortable ambient laboratory conditions via mercury sphygmomanometry or an automatic blood pressure monitor. Heart rate will also be determined by an automatic blood pressure cuff. Measurements will conform strictly to American Heart Association guidelines.

Body Mass: Body weight will be measured on a digital scale accurate to +/- 0.01 kg.

Dietary intake analysis (24-hour recall): Subjects will be asked to recall all the food and beverages they consumed in the previous 24-hour period.

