Mixed Meal Tolerance Test: A small plastic tube (catheter) will be placed in one of the subject's arm veins. After a baseline blood draw to measure glucose, insulin, cholesterol, and other factors that may impact or be reflective of the subject's health status (e.g., C-reactive protein), the subject will drink a mixed meal beverage (Ensure original plus ®, 350 calories, 48g carbohydrate, 11g fat, and 16g protein) and blood will be collected in small amounts (less than one half teaspoon) at timepoints 0, 30, 60, 90, and 120 over a two-hour period.

Continuous Glucose Monitoring: The device which was placed on the subject will be removed.

Choline Supplement/Placebo: Subjects will be given enough capsules to last one week and asked to consume 1000 mg (2 x 500 mg tablets) of choline or placebo with a bottle of water every day.

Sessions 5-7, 14-16: (Approximately 30 minutes per session) Garvin Bldg, Suite 1575

Choline Supplement/Placebo: Subjects will be given enough capsules to last one week and asked to consume 1000 mg (2 x 500 mg tablets) of choline or the placebo with a bottle of water every day.

Resting Blood Pressure and Heart Rate: Blood pressure measurements will be made under quiet, comfortable ambient laboratory conditions via mercury sphygmomanometry or an automatic blood pressure monitor. Heart rate will also be determined by an automatic blood pressure cuff. Measurements will conform strictly to American Heart Association guidelines.

Body Mass: Body weight will be measured on a digital scale accurate to +/- 0.01 kg.

Dietary intake analysis (24-hour recall): Subjects will be asked to recall all the food and beverages they consumed in the previous 24-hour period.

After session 10: Following this session, subjects will return to their normal activities for a two-week "washout".

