## 11.0 Study Timelines

11.1 *Describe:*

- *The duration of an individual subject's participation in the study (for example, 1 hour, 2-4 weeks, 3-5 years).*
- *The amount of time expected to enroll all study subjects (weeks, months, years, etc.)*
- *The amount of time expected for the investigators to complete this study including primary data analyses.*

The duration of an individual's participation in this study will be approximately 12 weeks, which will include 19 visits to the HNFE department at Virginia Tech and approximately 36 hours of their time. The actual time and frequency of the subject's visits will depend on their and the study staff's schedule.

Subjects will begin the study on a rolling basis, but this will take place across approximately 12 months.

The total amount of time expected to complete this study is approximately 24 months.

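### On the protocol's own counts the capsules run out at day 28, before the post-supplement glucose trace and mixed meal test, and the interval since the last capsule is neither bounded nor recorded.

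*Combined protocol and SAP*

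**What the plan says.** In section 8.1 each participant takes the assigned "supplement for four weeks and will consume 1000 mg (500 BID) of choline or placebo per day", and testing is organised as "two periods of three-day testing sessions before and after the four-week period of choline and placebo supplement".

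Section 8.2 gives the visit detail. Capsules are handed out under two headings: "Session 4, 10, 13, 19: (Approximately 3 hours" and "Sessions 5-7, 14-16: (Approximately 30 minutes per session". Under both, "Subjects will be given enough capsules to last one week". The post-supplement battery is sessions 8, 9 and 10 in the first period and 17, 18 and 19 in the second:

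- Sessions 8 and 17: oral glucose tolerance test (OGTT) and placement of the glucose sensor, of which 8.2 says "The device will be worn for 3-4 days".
- Sessions 9 and 18: blood chemistry, arterial stiffness, flow-mediated dilation and the start of a 24-hour urine collection.
- Sessions 10 and 19: mixed meal test and then sensor removal ("The device which was placed on the subject will be removed"). The capsule item comes after both.

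The two-week washout starts after session 10, and session 19 is the last visit. Section 11.1 adds that the time and frequency of "visits will depend on their and the study" staff's schedule. No window is given between sessions 7 and 8 or between 16 and 17. Section 21.1 plans a semi-annual report on treatment compliance, but no section describes a capsule count or a record of the last capsule.

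**The concern.** Section 2.2 attributes changes in insulin sensitivity, mixed meal tolerance and 24-hour glycaemic control to a rise in TMAO produced by choline. The last two are measured by the mixed meal test and the sensor trace. On the protocol's counts, both fall after the capsules have run out. If the effect fades in those days, the choline-placebo contrast is diluted, more for the later tests than for the OGTT. If the interval also differs between participants or periods, it adds noise that cannot be removed later, because nothing records it and the model in section 5.2 has no term for it.

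The trial exists mainly to supply effect sizes for a larger study (sections 1.0, 5.2 and 14.1). A diluted estimate would therefore carry into that study's sample size. Separately, capsules handed out at session 10 contradict a washout that starts at that visit.

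**Working it through.** **Supply.** Inputs: one week per dispensing and the session numbers (8.2); a four-week period (8.1).

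- Period 1: sessions 4, 5, 6, 7 = 4 x 7 = 28 days.
- Period 2: sessions 13, 14, 15, 16 = 4 x 7 = 28 days.

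Both reproduce the stated four weeks, leaving nothing over for sessions 8-10 or 17-19.

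**Literal dispensing.** Counting every session under the two headings gives 4 + 6 = 10 dispensings, or 70 days, against 2 x 28 = 56 needed. The extra 14 days are handed out at sessions 10 and 19, after that visit's tests, so they do not cover the battery. If taken, the session 10 week would occupy 7 of the 14 washout days.

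**Total duration.** Section 11.1 gives about 12 weeks.

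- Batteries outside the 28 days: 56 + 14 + 4 x (3 to 4) = 82 to 86 days = 11.7 to 12.3 weeks.
- Post-supplement batteries inside the 28 days: 56 + 14 + 2 x (3 to 4) = 76 to 78 days = 10.9 to 11.1 weeks, or 11.4 to 11.7 with 4 screening days added.

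The first fits better, but the stated figure is too approximate to decide.

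**Time since the last capsule.** Take session 4 as day 0, with dosing starting on day 0 or 1, so the last dose is on day 27 or 28. Let session 8 fall on day 28 + g, where g is a delay that the documents do not limit. Session 10 falls 2 days after session 8 if the three visits are consecutive, and 3-4 days after it if the sensor wear time governs.

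| | OGTT (session 8) | Mixed meal and sensor removal (session 10) |
|---|---|---|
| General | g to g + 1 days | g + 2 to g + 5 days |
| g = 0 | 0-1 days | 2-5 days |
| g = 7 (assumption) | 7-8 days | 9-12 days |

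**Dilution, illustrative only.** The documents give no offset rate. If an effect decayed with half-life h hours, the fraction left after t hours would be 0.5^(t/h), and the mean over a 72-hour trace starting at the last capsule would be (1 - 0.5^(72/h)) / (0.693 x 72/h).

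| Assumed h | Left at 2 days | Mean over 72 h |
|---|---|---|
| 12 h | 6% | 24% |
| 24 h | 25% | 42% |
| 48 h | 50% | 62% |
| 7 days | 82% | 87% |

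Section 14.1 uses 20/32 = 0.625 for insulin sensitivity and expects similar magnitudes elsewhere. For a simple paired two-sided 5% test with n = 60, approximate power is Phi(0.625 x r x sqrt(60) - 1.96), where r is the fraction retained. For r = 1, 0.75, 0.5 and 0.25 this gives 99.8%, 95%, 68% and 23%. It concerns choline against placebo in everyone, not the comparison of age groups.

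**The case against.** The strongest reply is that testing off supplement is inferred, not stated. It rests on reading one summary sentence in 8.1 to the day. The washout begins only after session 10, which suggests that the battery belongs to the intervention phase. With session 7 on day 21, its supply lasts to day 28, and a battery on about days 25-28 would be covered. No day numbers exclude this. The shared heading for sessions 4, 10, 13 and 19 also looks like a grouped template, so counts taken from it may not be exact, and missed doses could leave capsules over.

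This limits the point to what the text implies if followed, but does not remove it. The covered reading conflicts with 8.1, which puts testing after the four weeks, and nothing in 8.2 states it. The scheduling sentence in 11.1 is general and does not cancel the three-day battery, but it is the only statement on visit timing and sets no window.

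Three stronger readings are tempting, and the documents do not support them:

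- A reader might infer that TMAO itself is measured off supplement. No visit procedure names TMAO. Blood is drawn at sessions 8, 9 and 10, so it could come from the first draw.
- A reader might infer that every hypothesised outcome is compromised. The OGTT, which bears on the insulin sensitivity used for the sample size, comes at the first post-supplement visit and is the least exposed.
- A reader might infer that the interval differs between young and older participants. Nothing in the documents shows this.

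**Conclusion.** The point holds as an internal inconsistency that should be reconciled. Followed literally, the protocol supplies 28 days of capsules per period and then runs the sensor trace and mixed meal test. With session 8 on day 28, the mixed meal falls about 2-5 days after the last capsule, with no upper limit if session 8 is delayed. The OGTT falls at about 0-1 days. These intervals assume weekly pick-ups and full adherence; day 28 is derived from the supply and is not stated. The dispensing at sessions 10 and 19 conflicts with the washout and the end of the study on any reading.

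How much the treatment contrast would shrink is unknown. The half-lives above are assumptions, range from near-trivial to severe dilution, and need not be the same for glycaemia, vascular function and plasma TMAO. They are not evidence that harm will occur.

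**What to change.** - Reconcile sections 8.1 and 8.2 so that the protocol states where the last capsule falls relative to sessions 8-10 and 17-19, and what, if anything, is dispensed at sessions 10 and 19. Which schedule is intended is for the sponsor.
- Record the date and time of the last capsule at each post-supplement session.
- Set one visit window for the post-supplement battery so that the interval is the same in both periods.
- If intervals still vary, add to section 5.2 a sensitivity analysis on post-supplement values with a treatment-by-time-since-last-capsule term. A main effect alone would not show dilution, because fading would shrink only the choline effect. The term is undefined at the first baseline and is set after randomisation, so it is supportive only. If the window is kept, it will have little variation to work on.

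The cost is schedule wording, one field on the data sheet and slightly less flexible visit booking.
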